### 4.8.1 pNf-H concentration and change in pNf-H

Baseline pNf-H concentrations will be summarized overall, by age of onset using descriptive statistics. Spearman correlation coefficients between baseline pNf-H and one of the baseline measurements (Baseline weight, Age at first dose, gestational age, HINE motor milestones score) and the corresponding  $p$ -values testing whether such correlation is equal to zero will be presented

Summary tables will be presented for pNf-H concentration, change and percentage change from baseline pNf-H by visit. A plot of mean over time will be presented for pNf-H concentration on the semi-logarithmic scale. The mean change from baseline and percentage change from baseline, respectively will be presented on the original scale.

#### **4.8.2 Change in CSF SMN protein concentration**

An appropriate assay for SMN protein in the CSF has not been identified. Once available, analyses will be performed to explore and characterize this across the study endpoints.

#### **4.9 Sibling SMA Data Collection**

If any subject has or had a sibling(s) with SMA and if consent is given, data for the sibling(s) will be collected at Day 1 and at the End of Study Evaluation/Early Termination Visit. Data to be collected from siblings with SMA will be non-biologic and noninvasive and will include historical data for SMN2 gene copy number and sibling treatment history.

Part of protocol amendment 4 incorporated retrospective and potential prospective capture of data on siblings of subjects enrolled into protocol 232SM202 who were affected by SMA. Depending on the amount and completeness of data collected it may be possible to perform some analyses comparing subjects in protocol 232SM202 who were dosed versus siblings. Differences in age at symptom onset, age at death and highest motor function attained between such siblings will be explored.

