5.1. Overview of Spinal Muscular Atrophy

SMA is an autosomal recessive neuromuscular disease characterized by degeneration of the motor neurons in the anterior horn of the spinal cord, resulting in atrophy of the voluntary muscles of the limbs and trunk. With an incidence of 1:6000 to 1:10,000 live births, SMA is the most common genetic cause of infant mortality, and a major cause of childhood morbidity due to weakness, in developed countries. The natural history of SMA includes 4 major recognized phenotypes that are dependent on age of onset and achieved motor abilities. The most severe form, Type I SMA, has a disease onset within the first few months of life; these children are never able to sit or walk and usually die from respiratory failure by the age of 2 years. Patients with Type II SMA are able to sit but never walk unaided, with symptoms typically presenting between 6 and 18 months of age. Patients with Type III SMA are able to sit and walk but may become severely and increasingly disabled. Patients with Type IV or adult-onset SMA have an age of onset over 18 years and have normal life expectancies.

SMA is caused by loss of SMN protein due to a homozygous deletion or mutation or compound heterozygous mutation in the *SMN1* gene on chromosome 5q11-q13. Humans have a duplication of the chromosome region where *SMN1* is found, resulting in a second copy of the gene, *SMN2*. In *SMN2*, a C to T nucleotide substitution in exon 7 results in an alternative splicing event such that the majority of transcripts produced (~90%) lack exon 7, and a defective truncated protein is produced. The remainder, *SMN2* transcripts containing exon 7, produces a full-length protein product identical to the SMN1 protein, since the C to T substitution is silent. Humans have a variable copy number of the *SMN2* gene (0 to 8 copies) [Wirth 2006]. The number of *SMN2* copies and the resulting amount of full-length SMN protein expressed in patients with SMA (10% to 40% of normal SMN protein levels) correlate with SMA disease severity; thus, *SMN2* is a key modifier of disease phenotype [Covert 1997; Feldkötter 2002; Lefebvre 1997; Prior 2004].

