8. SELECTION OF SUBJECTS

8.1. Inclusion Criteria

To be eligible to participate in this study, candidates must meet the following eligibility criteria at Screening or at the time point specified in the individual eligibility criterion listed:

1. Ability of parent(s) or legal guardian(s) to understand the purpose and risks of the study and provide signed and dated informed consent and authorization to use confidential health information in accordance with national and local subject privacy regulations.
2. Genetic documentation of 5q *SMA* homozygous gene deletion, mutation, or compound heterozygote.
3. Onset of clinical signs and symptoms consistent with SMA at ≤ 6 months of age and have documentation of 3 *SMN2* copies.

OR

Onset of clinical signs and symptoms consistent with SMA at ≤ 6 months of age, > 7 months of age (211 days) at screening, and have documentation of 2 *SMN2* copies.

OR

Onset of clinical signs and symptoms consistent with SMA at > 6 months of age, are ≤ 18 months of age at screening, and have documentation of 2 or 3 *SMN2* copies.

4. Meets age-appropriate institutional criteria for use of anesthesia/sedation, if use is planned for study procedures (as assessed by the Investigator and either the anesthesiologist or pulmonologist).
5. Medical care, such as routine immunizations (including influenza vaccine, pneumococcus vaccine, and respiratory syncytial virus prophylaxis [palivizumab] if available), meets and is expected to continue to meet guidelines set out in the Consensus Statement for Standard of Care in SMA, in the opinion of the Investigator.
6. Subjects with 2 *SMN2* copies must reside within approximately 9 hours' ground-travel distance from a participating study site for the duration of the study. Residents who are > 2 hours' ground-travel distance from a study site must obtain clearance from the Investigator and the study Medical Monitor.
7. Able to complete all study procedures, measurements, and visits, and parent or legal guardian/subject has adequately supportive psychosocial circumstances, in the opinion of the Investigator.

For Part 2 only:

To be eligible to participate in Part 2 of this study, candidates must meet the following eligibility criteria at the time of consent to participate in Part 2:

1. Participation in Part 1 and completion of the End of Part 1 Evaluation assessments.

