8.2. Exclusion Criteria

Candidates will be excluded from study entry if any of the following exclusion criteria exist at Screening or at the time point specified in the individual criterion listed:

1. Any previous exposure to Nusinersen; previous dosing in this study or previous studies with Nusinersen.
2. Signs or symptoms of SMA present at birth or within the first week after birth.
3. Ventilation for ≥ 16 hours per day continuously for >21 days at screening.
4. Permanent tracheostomy, implanted shunt for CSF drainage, or implanted CNS catheter at screening.
5. History of brain or spinal cord disease that would interfere with the LP procedure, CSF circulation, or safety assessments.
6. Hospitalization for surgery (e.g., scoliosis surgery), pulmonary event, or nutritional support within 2 months prior to screening, or hospitalization for surgery planned during the study.
7. Clinically significant abnormalities in hematology or clinical chemistry parameters or ECG, as assessed by the Investigator, at the Screening Visit that would render the subject unsuitable for inclusion.
8. Treatment with an investigational drug for SMA (e.g., albuterol/salbutamol, riluzole, carnitine, sodium phenylbutyrate, valproate, hydroxyurea), biological agent, or device within 30 days prior to screening. Any history of gene therapy, prior ASO treatment, or cell transplantation.
9. Ongoing medical condition that according to the Investigator would interfere with the conduct and assessments of the study. Examples are medical disability (e.g., wasting or cachexia, severe anemia) that would interfere with the assessment of safety or would compromise the ability of the subject to undergo study procedures.
10. The subject's parent or legal guardian is unable to understand the nature, scope, and possible consequences of the study, or does not agree to comply with the protocol's schedule of assessments.
11. Subject's parent or legal guardian is not willing to continue to meet standard of care guidelines for care (including vaccinations and respiratory syncytial virus prophylaxis if available), nor provide nutritional and respiratory support throughout the study.
12. Other unspecified reasons that, in the opinion of the Investigator or the Sponsor, make the subject unsuitable for enrollment.

CONFIDENTIAL

The information contained herein may not be used, disclosed, or published without the written consent of Biogen MA Inc.

For Part 2 only:

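### The sibling comparison in SAP 4.9 is not aligned to age at entry and does not use sibling treatment history; unaligned survival favours dosed children even with no drug effect

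*SAP*

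**What the plan says.** SAP 4.9 introduces the comparison conditionally. "Depending on the amount and completeness of data collected", it says, "it may be possible to perform some analyses comparing subjects in protocol 232SM202 who were dosed versus siblings". It then names the contrasts: "Differences in age at symptom onset, age at death and highest motor function attained between such siblings will be explored". A sibling enters on a wide condition: "If any subject has or had a sibling(s) with SMA and if consent is given". Dead siblings are therefore included, with no age or survival requirement. The items named for collection are "historical data for SMN2 gene copy number and sibling treatment history".

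Section 4.9 gives no starting age, censoring rule, age for the motor comparison or rule for treated siblings. Nor does it say when a Part 1 sham child counts as dosed. SAP section 2 uses the first dose or sham procedure as the time origin for time-to-event endpoints, a date that siblings do not have. Protocol 16.3.2.1 covers collection of sibling data only.

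Trial children, by contrast, passed entry conditions (Protocol 8.1 and 8.2). One eligibility route (onset at 6 months or earlier, 2 SMN2 copies) requires "> 7 months of age (211 days) at screening". Exclusions include "Permanent tracheostomy, implanted shunt for CSF drainage, or implanted CNS catheter at screening", prolonged ventilation of 16 hours or more a day, and signs of SMA in the first week of life.

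**The concern.** The two groups are put under observation by different rules. A sibling who died at 5 months can be counted. A trial child on the 2-copy, early-onset route cannot have died at that age. This is the usual immortal-time problem with an external comparator.

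The schedule strengthens it. The sibling row appears in Protocol Tables 3 and 4 (Part 2 Day 1 and the final or early-termination visit) and not in Table 2 (Part 1). Part 2 also requires a completed End of Part 1 Evaluation. A child with sibling data has therefore normally survived to Part 2 Day 1. If dosed means given nusinersen, a sham child who died in Part 1 drops out of the comparison.

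Treated siblings are a separate matter. Protocol 5.2 records commercial approval in the US from December 2016 and later in Europe, so a sibling may have had the drug.

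Age at symptom onset precedes entry in this symptomatic population, and the first-week exclusion truncates it. It describes comparability; the trial treatment cannot affect it.

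At stake is the reading of an exploratory contrast. A survival difference produced by selection could be taken for benefit.

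**Working it through.** The documents give no figure for the sibling comparison, so there is nothing to reproduce. The check asks what an unaligned comparison would show under no drug effect.

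**Inputs.** Entry age: 7 months from Protocol 8.1, with 1, 12 and 18 months as alternatives. Untreated survival: Protocol 5.1 says only that children with the most severe form "usually die from respiratory failure by the age of 2 years". No rate is given, so survival at 24 months, S(24), is assumed to be 0.20 or 0.40 for severe disease and 0.80 or 0.95 for milder disease. Survival is taken as Weibull with shape k = 0.7, 1.0 or 1.5, also an assumption.

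**Survival.** Siblings are counted from birth: S(24). Trial children are counted given survival to entry age a: S(24)/S(a) = S(24)^(1 − (a/24)^k).

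For S(24) = 0.20 and a = 7:
- k = 1.0: 0.20^(1 − 7/24) = 0.20^0.708 = 0.320, a gain of +12.0 points
- k = 0.7: 0.3945, a gain of +19.45 points
- k = 1.5: 0.2577, a gain of +5.8 points

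The apparent gain in points, over the three shapes:

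| S(24) | entry 1 month | entry 7 months | entry 12 months | entry 18 months |
|---|---|---|---|---|
| 0.20 | 0.3 to 3.8 | 5.8 to 19.45 | 15.3 to 33.9 | 36.9 to 54.6 |
| 0.40 | 0.3 to 4.2 | 6.2 to 18.9 | 15.3 to 30.3 | 32.5 to 44.6 |
| 0.80 | 0.2 to 2.0 | 2.9 to 7.9 | 6.6 to 11.8 | 12.5 to 16.0 |
| 0.95 | 0.0 to 0.5 | 0.8 to 2.1 | 1.7 to 3.1 | 3.2 to 4.1 |

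The later columns bear on children counted only from Part 2. If a sham child entered at 7 months and spent the full planned 14 months in Part 1, counting starts at 7 + 14 = 21 months. With S(24) = 0.20 and k = 1, S(36) from birth is 0.20^1.5 = 0.089, against S(36)/S(21) = 0.366. Part 1 stopped early, so 14 months is an upper bound.

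**Other contrasts.** A simulation used 200,000 sibling pairs with no drug effect, a shared gamma frailty (variance 0.5, assumed), trial follow-up of 14 or 42 months, and siblings observed to 12, 36 or 120 months. At entry 7 months:
- Survival at 24 months with S(24) = 0.20: about +10 points, close to the closed form.
- Age at death among those who died: −43 to +22 months. Trial deaths are seen only within the follow-up window.
- Highest motor function, on a hypothetical 26-point score that rises with age: −2.4 to +4.3 points. It is negative when siblings were observed to an older age.

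Requiring the sibling to be alive at the trial child's entry age, with the same end of observation, brought the survival difference within 0.6 points of zero and the motor difference within 0.03 points of zero.

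**Treated siblings.** If a fraction f of siblings is treated with equal benefit, a true effect D appears as D(1 − f). For D = 20 points this is 15 at f = 0.25 and 10 at f = 0.50. For D = 0 it stays 0.

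**The case against.** The strongest reply is that 4.9 is a conditional remark within an exploratory section. It fixes no estimator, test or time origin, and collection is optional and depends on consent in a trial of at most 21 children. That stands as a limit on importance. It does not remove the point: the condition in 4.9 concerns the amount and completeness of data, not comparability, and the contrasts are named.

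A reader might infer that the analysis must show both a survival and a motor gain without any drug effect. The documents do not support that. Counting siblings from birth is the natural reading of age at death with no entry age, but it is not written. The motor contrast can go either way.

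A reader might also infer that treated siblings inflate the result. They dilute it.

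It is tempting to say that selection alone makes trial children die about 7 months later on average. That follows only from an assumed exponential with unlimited follow-up. Planned participation is about 43 months, and the SAP says Part 2 ends early.

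Nor is this the only comparison without drug. Part 1 has its own SAP, and the integrated efficacy displays keep the Part 1 control period as a group. Finally, 4.9 does not call age at onset an outcome; it lists it beside two outcomes without distinction.

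**Conclusion.** The point holds as a defect in a named exploratory comparison. Without alignment to age at entry, survival is biased toward the dosed children under no drug effect. The size depends on the subgroup:
- Roughly 6 to 20 points at 24 months for severe disease with entry at 7 months (S(24) = 0.20), and more if counting starts later.
- About 1 to 8 points for milder disease with the same entry age.
- 0 to 4 points for entry at 1 month, which the route with 3 SMN2 copies and onset at 6 months or earlier allows because it sets no minimum age.

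These figures rest on assumed survival rates and Weibull shapes; the documents give neither.

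No direction can be claimed for highest motor function or for age at death among those who died. Treated siblings bias a real effect toward zero and add nothing under no effect. The safety analyses and the randomised Part 1 comparison are untouched. A correction before the analysis is run is worthwhile because the data for the main step, age at death and treatment history, are already in view.

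**What to change.** Replace the last two sentences of SAP 4.9 with rules to this effect:

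- Any sibling comparison is descriptive.
- Age is the time scale, left-truncated at the trial child's age when sibling data become available (Part 2 Day 1 on the schedule), or at first nusinersen dose if later.
- Only siblings alive at that age are included, and free of tracheostomy or permanent ventilation where this is known.
- Each pair has a common end of observation.
- Siblings given an SMN-targeted therapy are excluded, or censored at its start.
- Motor function is compared at matched ages only.
- The SAP states when a Part 1 sham child counts as dosed.
- Age at onset and SMN2 copy number are reported as comparability variables, not outcomes.
- If no pair qualifies, the data are listed and no comparison is made.

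The cost is SAP wording, some programming and fewer usable pairs. Sibling ventilation status and dated motor function are not among the items named as collected. The ventilation condition therefore applies only where the information exists, and the motor comparison may reduce to a listing.

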#### **4.10 Interim Analyses**

No formal interim analyses will be conducted.

### **5 Safety Data**

Analyses of safety data will include adverse events (Section 5.1), laboratory data (Section 5.2), ECGs (Section 5.3), vital signs (Section 5.4), and neurological examinations (Section 5.5).

Analyses of safety data will be based on the Safety Set. Baseline is defined as the last non-missing results prior to the first dose of Nusinersen or sham procedure.

#### **5.1 Clinical adverse events**

All adverse events will be analyzed based on the principle of treatment emergence. An adverse event will be regarded as treatment emergent if it was present prior to receiving the first dose of Nusinersen or sham procedure and subsequently worsened in severity, or was not present prior to receiving the first dose of Nusinersen or sham procedure but subsequently appeared. For subjects receiving the sham procedure in Part 1, an additional treatment emergent definition will be used to define if the adverse event is treatment emergent to the first dose of Nusinersen in Part 2.

In the situation where change in severity (but no change in seriousness) occurs for an adverse event, study sites are instructed to enter an end date and start a new record for the adverse event. In the new record, the changed severity is to be recorded and the start date will be set to be the end date of the previous record. These records will be programmatically linked by preferred term and start/end date. Consider three scenarios:

- The first AE record occurs prior to the first dose, the second AE record occurs on or after the first dose, and the severity increases: only the second record will be counted as treatment-emergent.
- The first AE record occurs prior to the first dose, the second AE record occurs on or after the first dose, and the severity decreases: neither record will be counted as treatment-emergent.
- Both records occur on or after the first dose: if the AE severity on the second record is worse than the severity on the first record, then both records will be counted as treatment-emergent. However, if the severity decreases, then only the first record will be counted as treatment-emergent.

Of note, when counting the total number of treatment-emergent events, events linked through change in severity will still be counted as separate events.

For events with missing start or stop dates, the following criteria will be used for the purpose of identifying treatment-emergent adverse events:

- if both the start and stop dates for a particular event are missing, then the event is considered to have occurred on or after the first dose of study treatment;
- if the start date for a particular event is missing and the stop date/time falls after the first dose date/time, then the event is considered to have occurred on or after the first dose of study treatment; and
- if the start time is missing and the start date is same as the first dosing date, then the event is considered to have occurred on or after the first dose of study treatment.

If it cannot be determined whether an event has occurred on or after dosing due to a missing or partial date, then the event will be assumed to have occurred on or after the first dose for the purpose of identifying treatment-emergent AEs.

Due to the long half-life of Nusinersen, analyses of treatment-emergent AEs will include all events reported during the study.

AEs will be coded using the MedDRA dictionary. This coding system provides more than five levels to classify adverse events. In general, adverse events will be presented by system organ class and preferred terms but other classifications may be used if warranted.

The incidence of treatment-emergent AEs will be summarized. A subject having the same AE more than once will be counted only once in the incidence for that AE. The summary tables will include incidence estimates for overall system organ class as well as for preferred terms within each system organ class. Incidence will be presented by decreasing order by system organ class and by decreasing order by preferred term within each system organ class. The most common AEs, i.e., those that occurred in at least 3 subjects, will be presented. Upon examination of the actual data, different cut-offs may be used if it is deemed more appropriate.

#### **5.1.1 Adverse events by severity**

The investigator is to record the severity of each adverse event as mild, moderate, or severe. If a subject experiences the same AE multiple times, the event with the worst severity will be counted. The incidence within each category will be presented. The incidence of severe events will be summarized.

#### **5.1.2 Adverse events by relationship to study treatment**

The investigator is to record the degree to which each AE is related to study drug (not related, unlikely or remotely related, possibly related, and related). If a subject experiences the same AE multiple times, the event with the strongest relationship to study drug will be counted. The incidence within each category will be presented. The incidence of drug-related events (those categorized as possibly related or related) will be summarized.

#### **5.1.3 Serious adverse events**

The incidence of treatment-emergent SAEs will be summarized by time of onset by 3-month time intervals. All SAEs will be listed including any that occurred prior to commencement of study treatment.

#### **5.1.4 Adverse events that led to discontinuation from treatment and/or withdrawal from study**

The incidence of AEs that led to discontinuation of study treatment and those that led to withdrawal from the study will be presented.

### **5.1.5 Deaths**

The incidence of death will be summarized. All deaths will be listed including cause of death. The incidence of events that led to death will be presented.

### **5.1.6 Presentations**

The following presentations will be shown for the integrated analysis:

- an overall summary showing, the number and percentage of subjects with an AE, a moderate or severe event, a severe event, a possibly or related event, a related event, a serious event, an event that led to discontinuation of study drug, and an event that led to withdrawal from the study, repeated also by age at symptom onset
- incidence by primary system organ class and preferred term, repeated also by age at symptom onset
- Frequency of adverse events by system organ class and preferred term, repeated also by age at symptom onset
- incidence of mild, moderate and severe events by primary system organ class and preferred term
- incidence of severe events by primary system organ class and preferred term
- incidence of not related, unlikely to be related, possibly related, and related events by primary system organ class and preferred term
- incidence of drug-related events by primary system organ class and preferred term
- incidence of SAEs by primary system organ class and preferred term and a listing of SAEs
- incidence of death and a listing of each death
- incidence of events that led to death
- incidence of events leading to discontinuation of study drug by primary system organ class and preferred term and a listing of such events
- incidence of events leading to withdrawal from the study by primary system organ class and preferred term and a listing of such events
- incidence of events of special interest – AEs following dosing procedure/LP, AEs by antibody status etc., by primary system organ class and preferred term and a listing of such events.

To avoid the potential for misleading interpretation of analysis of AEs, no statistical testing will be performed.

Only the following presentations will be shown for Part 2 analysis:

- an overall summary showing, the number and percentage of subjects with an AE, a moderate or severe event, a severe event, a possibly or related event, a related event, a serious event, an event that led to discontinuation of study drug, and an event that led to withdrawal from the study
- incidence by primary system organ class and preferred term
- Incidence of serious adverse events by primary system organ class and preferred term and a listing of SAEs.
- Frequency of adverse events by system organ class and preferred term

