## 1 Study Design

This is a Phase 2 multicenter study conducted in 2 parts.

Part 1 was originally designed as a randomized, double-blind, sham-procedure controlled study to assess the safety and tolerability and explore the efficacy of intrathecally administered Nusinersen (also known as ISIS 396443 and BIIB058) over a period of approximately 14 months (from the first dose until the End of Part 1 Evaluation). Up to 21 subjects were randomized in a ratio of 2:1 to receive Nusinersen by intrathecal lumbar puncture (LP) injection or a sham-procedure control. Randomization was stratified based on age at onset of clinical signs and symptoms consistent with SMA: >6 months versus ≤6 months. Part 1 of the study was stopped early due to the efficacy results seen in the ISIS 396443-CS3B study and the planned analysis of Part 1 is described in a separate Statistical Analysis Plan and corresponding CSR.

Part 2 study procedures will be determined based on the treatment assignment in Part 1.

For subjects who were randomized to receive Nusinersen in Part 1, Part 2 Day 1 will occur following the End of Part 1 Evaluation or approximately 4 months following the last injection of Nusinersen in Part 1. On Part 2 Day 1, subjects will undergo predose evaluations according to the schedule of events and then receive their first dose of Nusinersen for Part 2 (next maintenance dose). Subjects will return to the study site on Days 120, 239, 358, 477, 596, and 715 for follow-up evaluations and subsequent maintenance dose injections. For subjects who were receiving sham procedure in Part 1, Part 2 Day 1 will occur following the End of Part 1 Evaluation or as soon as possible following the End of Part 1 Evaluation. At Day 1, subjects will undergo predose evaluations according to the schedule of events and then receive their first dose of Nusinersen (first loading dose). Subjects will return to the study site on Days 15, 29, 64, 183, 302, 421, 540, 659, and 778 for follow-up evaluations and subsequent injections. All subjects will terminate early Part 2 for enrollment in open-label extension study, ISIS 396443-CS11.

This statistical analysis plan (SAP) describes the analyses planned for the entire study (integration of Part 1 and Part 2) and additionally some summaries of Part 2 data only.

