Summary statistics will be presented throughout. For continuous endpoints, summary statistics will generally include number of subjects with data, mean, standard deviation, median, minimum and maximum. The mean changes from baseline will be estimated with 95% confidence intervals. For categorical endpoints, summary statistics will generally include: number of subjects dosed, number of subjects with data, and the percentage of those with data in each category. Frequency distributions will be presented as appropriate.

The statistical software, SAS® version 9.4 or above, will be used for all summaries and statistical analyses.

For Part 2, a limited number of summaries will be produced. The approach will be to preserve the Part 1 study groupings as follows for Safety and Efficacy population:

- Previous control.
- Previous ISIS 396443.
- Total (previous control and previous ISIS 396443).

For the integrated analyses, the Safety displays will be grouped as follows:

- Previous control, Part 1, from their first sham procedure in Part 1.
- Previous control, Part 2, from their first ISIS 396443 dose in Part 2.
- Previous ISIS 396443, Part 1 and 2, from their first ISIS 396443 dose in Part 1.
- Total (Previous control Part 2 and previous ISIS 396443 Part 1 and 2)

For the integrated analyses, the Efficacy displays will be grouped as follows:

- Previous control, Part 1, from their first sham procedure in Part 1.
- Previous control, Part 2, from their first ISIS 396443 dose in Part 2.
- Previous control, Part 1 and 2, from their first sham procedure in Part 1.
- Previous ISIS 396443, Part 1 and 2, from their first ISIS 396443 dose in Part 1.

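### The planned incidence of AEs following the dosing procedure or lumbar puncture reads as a share of children, but the integrated columns hold different numbers of procedures per child, so the shares do not compare procedure risk

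*SAP*

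**What the plan says.** For the integrated analysis, SAP 5.1.6 (Presentations) plans an incidence display for special-interest events. The bullet covers "AEs following dosing procedure/LP, AEs by antibody status etc., by primary system organ class and preferred term and a listing of such events". SAP 5.1 fixes how incidence is counted: "A subject having the same AE more than once will be counted only once in the incidence for that AE". SAP 5.1.6 does not state a denominator for this table, so the share-of-children reading comes from putting the two sections together.

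SAP 2 sets four integrated safety columns. The first holds the sham group during Part 1, counted from the first sham. The second holds the same children after they switch to active drug, defined as "Previous control, Part 2, from their first ISIS 396443 dose in Part 2". The third holds the children randomized to nusinersen, followed through both parts from the start of treatment. The fourth is a pooled column that adds the second and third and leaves out the sham period.

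No section of this SAP states how soon after a procedure an AE must start to count as following it, and none plans a rate per procedure. SAP 3.3 tabulates the number of doses and sham procedures as exposure. SAP 5.1.6 also plans a frequency table for all AEs and states that AEs will not be tested statistically.

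**The concern.** An AE that follows a procedure needs a procedure to follow, so each procedure is a fresh opportunity. If one column gives each child more procedures than another, a larger share of its children will have at least one such AE even when the risk per procedure is identical. Conversely, equal shares can hide unequal risks.

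This matters because safety and tolerability are the primary objective of both parts (SAP, Primary Objectives and Endpoints; Protocol 6.1). This is also the table in which a reader would look for the burden of repeated lumbar puncture. Protocol 5.3.2 reports post-lumbar-puncture syndrome as the most common AE in an earlier multiple-dose study of nusinersen.

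**Working it through.** **Inputs**

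- Part 1, both arms: Days 1, 15, 29, 64, 183 and 302 (SAP 1.2), which is 6 procedures. Protocol 7.2.2 states a Part 1 total of 6, so the count reproduces the plan's own figure.
- Previous control, Part 2: the first dose on Day 1, then "Subjects will return to the study site on Days 15, 29, 64, 183, 302, 421, 540, 659, and 778" (SAP 1). That is 1 + 9 = 10.
- Previous nusinersen, Part 2: Day 1, then Days 120, 239, 358, 477, 596 and 715 (SAP 1). That is 1 + 6 = 7, and 6 + 7 = 13 over both parts.
- Planned children: 14 nusinersen and 7 sham (Protocol 7.1).
- Procedure type: the sham is a skin prick without a lumbar puncture (Protocol 11.1.2), so only the second and third columns are like for like.
- Risk per procedure, p: not given in the documents. It is assumed, equal in both columns, and shown over a range.

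**Share of children with at least one event**

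With m independent procedures per child, the share is 1 − (1 − p)^m.

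| p | m = 10 (previous control, Part 2) | m = 13 (previous nusinersen) | Ratio |
|---|---|---|---|
| 2% | 18.3% | 23.1% | 23.1/18.3 = 1.26 |
| 5% | 40.1% | 48.7% | 48.7/40.1 = 1.21 |
| 10% | 65.1% | 74.6% | 74.6/65.1 = 1.15 |

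**Absolute scale**

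At p = 5% the gap is 48.7 − 40.1 = 8.6 percentage points. One child in a column of 7 is 1/7 = 14.3 points.

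**Reverse direction**

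If 40% of children had an event in each column, the implied risk per procedure would be 1 − 0.6^(1/10) = 4.98% in one and 1 − 0.6^(1/13) = 3.85% in the other.

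**Clustering**

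Keep the average risk at 5%, but let half the children carry 10% and the rest none. The shares become 0.5 × 65.1 = 32.6% and 0.5 × 74.6 = 37.3%. The ratio falls from 1.21 to 1.15.

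**Early stopping**

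Delivered counts are not in the documents. These are assumed counts (sham, previous control Part 2, previous nusinersen) at p = 5%:

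| Assumed counts | Shares | Ratio of the two LP columns |
|---|---|---|
| 6, 8, 11 | 26.5 / 33.7 / 43.1% | 1.28 |
| 5, 7, 10 | 22.6 / 30.2 / 40.1% | 1.33 |
| 4, 4, 8 | 18.5 / 18.5 / 33.7% | 1.82 |

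The LP contrast can therefore be wider than on the full schedule. In the last row the first two columns do not differ at all.

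**With procedures as the denominator**

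At full enrolment and on the full schedule, the denominators would be 7 × 6 = 42 sham pricks, 7 × 10 = 70 LPs and 14 × 13 = 182 LPs (252 LPs in the Total). Equal risk then gives the same expected rate in every LP column. Procedures actually performed must replace these counts.

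**The case against.** The case for leaving the plan alone has weight. Dose and sham counts are tabulated, an all-AE frequency table is planned, the disputed bullet includes a listing, and nothing is tested. With at most 21 children, a reader could relate listed events to procedures. On the full schedule, the distortion between the two LP columns is smaller than one child in the column of 7. The randomized comparison with sham, 6 scheduled procedures in each arm, belongs to a separate Part 1 SAP that is not among these documents and might define the interval. These points limit the size of the problem. They do not supply a rate per procedure: the exposure table is not linked to AEs, the frequency table is neither restricted to AEs after a procedure nor divided by procedures, and a listing leaves the calculation to the reader.

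Three stronger readings are tempting and are not supported.

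- **Procedure count alone makes previous nusinersen look 1.6 to 2.0 times worse than sham.** The same formula gives this for 13 against 6 procedures at 10% down to 2%. It requires a skin prick and a lumbar puncture to carry equal risk, which Protocol 11.1.2 gives no reason to assume; part of any difference from sham may be real.
- **The table must rank sham lowest, previous control Part 2 next and previous nusinersen highest.** SAP 1 says both parts end early, and SAP 2 says sham subjects left Part 1 first, regardless of planned dosing days. The order of the first two columns depends on delivered counts.
- **An AE months after a lumbar puncture counts as following it.** The statement that "analyses of treatment-emergent AEs will include all events reported during the study" concerns treatment emergence and rests on the drug's long half-life. It does not define AEs following a procedure. The supportable point is only that the interval is undefined.

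**Conclusion.** The point holds as a cheap improvement. Read as a share of children, the planned incidence cannot be compared between integrated columns as a measure of procedure risk. On the full schedule, the like-for-like LP contrast is inflated by about 1.15 to 1.26 times. That range rests on a risk per procedure of 2% to 10%, equal in both columns and independent between procedures; none of this comes from the documents. Clustering of events within children lowers the factor, and early stopping can move it. No single size can be given for the contrast with sham, because it mixes procedure types and depends on procedures delivered. The affected output is one descriptive table in a small study.

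**What to change.** Keep the bullet as it stands, because it also carries AEs by antibody status and the listing, and keep the incidence per child. Add to SAP 5.1.6:

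> For AEs following the dosing procedure/LP, defined as onset within a prespecified interval after a procedure (for example 7 days, with a 3-day version listed), present the number of procedures followed by at least one such AE divided by the number of procedures actually performed, by column and procedure type (sham prick or LP), beside the number of children. Descriptive only, noting repeated procedures within a child.

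The 7-day and 3-day intervals are examples without a basis in the documents; what matters is that an interval is fixed in advance. The cost is one sentence and one derived variable. No new data are needed: dosing details go on the Dosing CRF (Protocol 15.4.1) and investigators determine AE onset dates (Protocol 15.5.1). The small downside is having to choose an interval.
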